### **4.3.3 Other safety variables**

Other safety variables to be assessed are:

- Change from Baseline in clinical laboratory values (chemistry, hematology, and urinalysis)
- Change from Baseline in vital signs

- Change from Baseline in physical examination
- ECG results

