### **14.3.3 Planned safety and other analyses**

#### **14.3.3.1 Safety analyses**

All safety variables will be analyzed for all subjects in the SS.

Adverse events will be coded according to the Medical Dictionary for Regulatory Activities (MedDRA®). Treatment-emergent adverse events (TEAEs) will be summarized descriptively by treatment group, primary system organ class, high level term, and preferred term. Additional tables will summarize TEAEs by intensity and relationship to study drug, TEAEs leading to withdrawal from the study, treatment-emergent SAEs, and deaths.

Treatment-emergent adverse events will be defined as events that have a start date on or following the first administration of study treatment up until the final administration of study treatment +140 days (covering the 20-week SFU Period). To allow for a fair comparison across all subjects, exposure at risk for defining treatment-emergence during the 28-week treatment period will be cut off at the Week 16 Visit (for subjects who complete through the Week 16 Visit) or at 20 weeks (140 days) after the last administration of study treatment (for subjects who discontinue prior to the Week 16 Visit).

Laboratory values, urinary values, ECGs, vital signs, and extent of exposure will be presented descriptively by treatment group.

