2.2.3.3 Other safety variables

Other safety variables to be assessed are:

- Change from Baseline in clinical laboratory variables (chemistry, hematology and urinalysis)
- Change from Baseline in vital signs
- Change from Baseline in physical examination
- Electrocardiogram (ECG) results

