4.2.2 Safety laboratory data

Measurements below the limit of quantification (BLQ) will be imputed with half of the lower limit of quantification (LLOQ) for the purpose of calculating change from Baseline and for descriptive statistics. Measurements above the limit of quantification (ALQ), if applicable, will be imputed to the upper quantification limit.

These rules will be applied to all numeric safety laboratory data including clinical chemistry, hematology and urinalysis variables.

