11.3 Clinical laboratory evaluations

Laboratory data (clinical chemistry, hematology, and urinalysis) and changes from Baseline (if applicable) for numeric variables will be listed by treatment group and visit. Any laboratory variables with values that are BLQ or ALQ will be handled as described in [Section 4.2.2](#) for calculation of changes from Baseline and for summary tables. Values outside the reference range for the numeric variables will be flagged in the listings and in addition, will be listed separately. The reference ranges will also be reported in the listings.

Clinical chemistry and hematology variables will be summarized by treatment group (including All Subjects) at each visit, for both absolute values and changes from Baseline.

Laboratory variables will be grouped according to the laboratory function panel and categorized as normal, high or low, if applicable, based on the reference range supplied by the analytical laboratory. For selected variables that are identified in [Table 11-1](#), the change in category from Baseline will be presented in shift tables at all post-Baseline visits.

The number and percentage of subjects with treatment-emergent markedly abnormal (TEMA) laboratory results (to match the TEAE definition stated in [Section 11.1.3](#)) will be tabulated by treatment group and visit. Markedly abnormal laboratory values will be defined as those categorized as Grade 3 and above based on the ranges defined as per the Common Terminology Criteria for Adverse Events (CTCAE) Version 4.03 (2016). These are provided in [Table 14-4](#). The tabulation will include a category for the incidence of TEMA results over all visits which will also count unscheduled measurements.

In addition, for absolute neutrophil count (ANC), all grade 2 CTCAE abnormalities ($<1.5 - 1.0 \times 10^9/L$) will be listed separately, with results from all visits for any subject that has any grade 2 abnormality.

Laboratory measurements meeting the criteria for TEMA will be listed separately for hematology and chemistry. The listings will include all measurements for any variable with at least one TEMA result for each subject.

Any additional laboratory variables not included in the outputs described previously will be listed separately. These will include the following:

- Serology
- Pregnancy tests (serum and urine)
- Follicle stimulating hormone (FSH) (only for postmenopausal women)

The results of the Quantiferon TB Gold test will be listed separately.

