Subjects with treatment-emergent liver function test abnormalities at any post-Baseline visit will be summarized (number and percentage of subjects) by treatment group. The criteria for this tabulation are presented in [Section 14.5](#).

Table 11–1: Clinical laboratory measurements

Category	Panel	Variable
Serology	Serology	HIV1-Ab, HIV2-Ab, HBsAg, anti-HBc, anti-HBs, anti-HCV-Ab, TB
Hematology	Red blood cell	RBC count ^a , hemoglobin, hematocrit
	Red blood cell indices	MCH, MCHC, MCV
	Platelet	Platelets
	White blood cell	WBC count ^a
	White blood cell differential	Absolute counts: ANC ^a , basophils, eosinophils, ALC, monocytes, atypical lymphocytes (if indicated) Percentages: neutrophils/leukocytes, basophils/leukocytes, eosinophils/leukocytes, lymphocytes/leukocytes, monocytes/leukocytes.
Chemistry	Electrolytes	Sodium, chloride, potassium, calcium, magnesium
	Kidney function	BUN, creatinine
	Liver function	AST ^a , ALT ^a , GGT ^a , ALP ^a , LDH ^a , total bilirubin (direct bilirubin, indirect bilirubin, if indicated)
	Lipids	Total cholesterol ^a
	Metabolic function	Glucose
	Hormones	FSH ^b
	Fertility	Pregnancy test ^c
	Other	CRP
Urinalysis	Dipstick	pH, protein, blood, leukocyte esterase, nitrite, glucose

Table 11–1: Clinical laboratory measurements

Category	Panel	Variable
	Urine sediment (if indicated)	WBC, RBC, epithelial cells (squamous, transitional and renal tubular), hyaline casts, WBC casts, RBC casts, waxy casts, granular casts, calcium oxalate crystals, uric acid crystals, triphosphate crystals, yeast, bacteria, amorphous urates, amorphous phosphates

ALC=absolute lymphocyte count; ALP=alkaline phosphatase; ALT=alanine aminotransferase; ANC=absolute neutrophil count; AST=aspartate aminotransferase; BUN=blood urea nitrogen; CRP=C-reactive protein; FSH=follicle stimulating hormone; GGT=gamma glutamyltransferase; anti-HBc= hepatitis B core antibody; anti-HBs=hepatitis B surface antibody; HbsAg=hepatitis B surface antigen; HCV-Ab=hepatitis C virus antibody; HIV1-Ab=human immunodeficiency virus 1 antibody; HIV2-Ab= human immunodeficiency virus 1 antibody; LDH=lactate dehydrogenase; MCH=mean cell hemoglobin; MCHC=mean cell hemoglobin concentration; MCV=mean cell volume; RBC=red blood cell; TB=tuberculosis; WBC=white blood cell.

^a Shift tables will be presented for these variables.

^b FSH performed on postmenopausal females who have been postmenopausal for ≥ 1 year and last menstrual cycle occurred < 2 years ago.

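### Urinalysis is a declared safety variable that the protocol promises to describe by arm, but SAP 11.3 plans only listings for it and SAP 3.9 does not declare the change

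*Protocol*

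**What the plan says.** Both documents declare the variable. Protocol 4.3.3 has "Change from Baseline in clinical laboratory values (chemistry, hematology, and urinalysis", and SAP 2.2.3.3 has "Change from Baseline in clinical laboratory variables (chemistry, hematology and urinalysis". Protocol 14.3.3.1 then states how it will be reported: "Laboratory values, urinary values, ECGs, vital signs, and extent of exposure will be presented descriptively by treatment group". Urine is named there separately from the other laboratory values. Protocol Table 5-1 schedules urinalysis at every visit.

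SAP 11.3 begins with all three panels: "Laboratory data (clinical chemistry, hematology, and urinalysis) and changes from Baseline (if applicable) for numeric variables will be listed by treatment group and visit". The next step, the summary tables, covers two of them: "Clinical chemistry and hematology variables will be summarized by treatment group (including All Subjects) at each visit". The shift tables are restricted to variables carrying footnote a of Table 11-1 ("Shift tables will be presented for these variables"). The dipstick row of that table reads "pH, protein, blood, leukocyte esterase, nitrite, glucose", and no entry in it carries the footnote.

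SAP 4.2.2, on values outside the quantification limits, says: "These rules will be applied to all numeric safety laboratory data including clinical chemistry, hematology and urinalysis variables". Its stated purposes are change from Baseline and descriptive statistics.

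**The concern.** A variable that is declared in both documents, and that the protocol promises to describe by arm, would normally have at least one table. Under SAP 11.3 as written, urinalysis has none, and nothing in the SAP says this was a decision.

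Safety and tolerability is a secondary objective of the trial. The arms are planned at about 30 and 15 subjects and the study is not powered for safety, so description by arm is the planned safety evidence. If protein, blood, leukocyte esterase or nitrite turned positive on treatment and the investigator did not record an adverse event, the report would give no count and no denominator of tested subjects. A reader would have to build both from the listings.

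**Working it through.** The plan gives no figure to reproduce here. The check traces each laboratory output in the SAP and asks whether urinalysis is in it.

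| Output | Place in SAP | Urinalysis included? |
|---|---|---|
| Data listing, with change from Baseline for numeric variables | 11.3 | Yes |
| Out-of-range flags and separate out-of-range listing | 11.3 | Yes, numeric variables only |
| By-visit summary of values and changes | 11.3 | No: chemistry and hematology only |
| Shift tables | 11.3, Table 11-1 footnote a | No: RBC, WBC, ANC, AST, ALT, GGT, ALP, LDH and total cholesterol only |
| Markedly abnormal values, table and listing | 11.3, Table 14-4 | No: hematology and chemistry only |
| Liver function abnormalities | 14.5 | Not applicable |

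Urinalysis therefore appears in the listings and in 0 aggregate laboratory tables. Change from Baseline and range flags apply to numeric variables, so a dipstick or sediment result reported as a category gets neither, even in the listings.

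Next, would a listing meet the protocol's undertaking? Protocol 14.2 describes summary statistics as frequency tables for categorical variables and the usual n, mean, SD, median and range for continuous ones. SAP 3.1 is to the same effect. The other items in the Protocol 14.3.3.1 sentence all receive tables: blood laboratory values (SAP 11.3), ECGs (11.4.3), vital signs (11.4.1) and exposure (11.1.2). Urinary values are the exception.

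Then, is the departure declared? SAP 3.9 gives three changes from the protocol: the Full Analysis Set definition, the spaghetti plots and the cut-off for treatment-emergent events. Urinalysis is not among them. Where the SAP intends a listing and no table, it can say so, as it does for body weight in 11.4.2.

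Last, the amount of data. The scheduled post-Baseline visits are Weeks 2, 4, 8, 12, 16, 20, 24, 28 and 36, which is 9. With 45 subjects the ceiling is 45 × 9 = 405 urinalysis panels (30 × 9 = 270 in arm A, 15 × 9 = 135 in arm B). This is an upper bound on samples, because subjects may withdraw or move to the extension study from Week 20. It does not measure bias or lost information. The arms also receive the same treatment up to the pre-dose Week 16 assessment, so a treatment-related difference between them could show at only 4 of the 9 visits (Weeks 20, 24, 28 and 36).

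**The case against.** The strongest reply is that the SAP's Introduction keeps the protocol's analysis in force wherever the SAP does not specify otherwise. SAP 11.3 nowhere says that urinalysis will not be summarised, so the omission is an inference from silence. Part of this stands: the text does not show a deliberate removal, and a reader should not infer one. But 11.3 does specify which panels are summarised, so the clause does not clearly restore the third. A programmer working from 11.3 would produce no urinalysis table.

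Four stronger readings are tempting, and the documents do not support them.

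- **No urine finding is ever counted by arm.** Protocol 12.1.1 includes abnormal laboratory findings in the definition of an adverse event, and SAP 11.2.3 tabulates treatment-emergent events by treatment group. Haematuria or proteinuria recorded as an adverse event is counted there. The gap concerns results that are not so recorded.
- **The reader cannot see the data.** The listings show all three panels by treatment group and visit. With about 45 subjects they can be read through, although they give no rates.
- **The SAP 4.2.2 rules serve nothing for urine.** They do have a use, because the 11.3 listing includes change from Baseline for numeric urinalysis. What lacks a planned use is their application to urinalysis descriptive statistics.
- **A between-arm comparison was dropped.** The protocol promised description only, and no formal comparison is planned for any laboratory variable.

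**Conclusion.** The point holds as an undeclared mismatch between protocol and SAP. Urinalysis is declared as a safety variable in both documents and is to be described by arm under Protocol 14.3.3.1, but SAP 11.3 gives it listings only. Urinalysis results not reported as adverse events have no aggregate summary by arm.

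The size is modest. One of the three laboratory panels in the declared variable is missing from every aggregate laboratory table. It is an other safety variable; the primary safety variable is the incidence of adverse events. The study is exploratory, and no primary or secondary efficacy result is affected. It is worth correcting because it departs from a written commitment and the remedy is cheap.

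The conclusion assumes that SAP 11.3 is carried out as written, and that presenting values descriptively by treatment group means summary statistics, as Protocol 14.2 and SAP 3.1 use that idea.

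**What to change.** In SAP 11.3, add a descriptive urinalysis summary by treatment group and visit:

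- for numeric variables such as pH, descriptive statistics of values and of change from Baseline;
- for the categorical dipstick results (protein, blood, leukocyte esterase, nitrite, glucose), frequency tables or Baseline-to-visit shift tables;
- as denominator, the subjects with a result at that visit.

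This restores the protocol's own analysis and gives the SAP 4.2.2 rules a summary to apply to. The cost is a paragraph of SAP text and one or two extra tables from data already collected.

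If the sponsor prefers listings only, the alternative is to declare and justify that in SAP 3.9 and bring 2.2.3.3 and 4.2.2 into line. That would remove the inconsistency but leave the panel without a summary.

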#### **4.3.4 RNA, proteins, and metabolite variables**

Blood and tissue biopsy samples will be collected at specific time points and stored for up to 20 years to allow for potential exploratory analyses of RNA, proteins, and metabolites biomarkers relevant to psoriasis and the inflammatory and immune response processes.

The nature and format of these tentative analyses will be determined at a later stage.

#### **4.4 Immunological variable**

The immunological variable is anti-bimekizumab antibody detection following study treatment.

### **5 STUDY DESIGN**

#### **5.1 Study description**

This is a Phase 2a, multicenter, randomized, subject-blind and investigator-blind study to evaluate the PD, PK, and safety of bimekizumab administered sc to subjects with psoriasis. To be eligible to participate in this study, subjects must be adults with a diagnosis of moderate to severe psoriasis (Baseline PASI  $\geq 12$  and BSA affected by psoriasis  $\geq 10\%$  and IGA score  $\geq 3$  [on a 5-point scale]) who are a candidate for systemic psoriasis therapy and/or phototherapy and/or chemophototherapy.

##### **5.1.1 Study Periods**

This study will include 3 periods: a Screening Period (up to 4 weeks), a Treatment Period (28 weeks), and a SFU Period (20 weeks after the last dose of study medication). Between Week 20 and the end of the 28-week Treatment Period, eligible subjects will be allowed to enroll in an extension study.

##### Screening Period

The Screening Period will last up to a total of 4 weeks in the event that applicable laboratory screening tests require retesting if the initial results are in error, borderline, or indeterminate. During this time, laboratory data (hematology, urine, and biochemistry tests) will be obtained, the doses of non-steroidal anti-inflammatory drug (NSAIDs) (if used to treat psoriatic arthritis), will be verified as stable.

##### Treatment Period

During the Treatment Period, subjects will be randomized 2:1 to receive the following blinded study treatment regimens:

- Treatment arm A: Bimekizumab 320mg administered sc at Baseline and Week 4, and placebo administered at Week 16
- Treatment arm B: Bimekizumab 320mg administered sc at Baseline and Weeks 4 and 16

There will be approximately 30 subjects in treatment arm A and 15 subjects in treatment arm B. Bimekizumab will be administered in the clinic at Baseline and Week 4, and at Baseline, Week 4, and Week 16 for those in treatment arm A and treatment arm B, respectively. Additional

nondosing study visits will occur at Week 2, Week 8, Week 12, Week 20, Week 24, and Week 28.

From Week 20 through Week 28, subjects who were previously PASI25 responders but subsequently relapse (defined as returning to a less than PASI25 response) will undergo the study assessments for that visit (ie, Week 20, Week 24, or Week 28) before receiving their first dose of study treatment in the extension study at Week 20, Week 24, or Week 28. Subjects eligible for the extension study must have the assessments for SFU conducted prior to entering the extension study. Subjects who have not achieved a PASI25 response at any visit prior to Week 20 will not be eligible to enter the extension study. All subjects not enrolling in the extension study will continue in PS0016 until the SFU Visit at Week 36.

Subjects withdrawing early from the study will undergo the Early Withdrawal Visit assessments (ie, Week 36) and will enter the SFU Period.

The assessments at each Treatment Period Visit are presented in [Table 5-1](#).

#### Safety Follow-Up Period

All subjects not continuing in the extension study, including those withdrawn from study treatment, will have a SFU Visit 20 weeks after their last dose of study medication (ie, bimekizumab or placebo).

The assessments for the SFU Visit are presented in [Table 5-1](#).

### **5.1.2 Study duration per subject**

For each subject, the study will last a maximum of up to 40 weeks. This includes the following study period durations:

- Screening Period: up to 4 weeks
- Treatment Period: 28 weeks
- Safety Follow-Up Period: a SFU Visit is planned 20 weeks after the last dose of study medication

The end of the study is defined as the date of the last visit of the last subject in the study.

### **5.1.3 Planned number of subjects and sites**

A sufficient number of subjects (anticipated to be approximately 90 subjects) will be screened in order to have approximately 45 subjects randomized in the study; 30 to Treatment arm A and 15 to Treatment arm B. The planned number of study sites is approximately 15.

### **5.1.4 Anticipated regions and countries**

The regions planned for study conduct are Europe and North America, with possible extension to other regions and countries.

## **5.2 Schedule of study assessments**

A schedule of study assessments is provided in [Table 5-1](#).

**Table 5–1: Schedule of assessments**

Visit a / Week  Protocol activity	Screening b	Baseline	Treatment Period (Time after the first dose)								Wk 36 EWD/ SFU c	
			Wk 2	Wk 4	Wk 8	Wk 12	Wk 16	Wk 20	Wk 24	Wk 28		
Informed consent d	X											
Inclusion/exclusion	X	X										
Demographic data	X											
Psoriasis history	X											
Significant past medical history and concomitant diseases e	X	X										
Physical examination	X											X
Height	X											
Body weight	X	X					X					X
Vital signs f	X	X	X	X	X	X	X	X	X	X	X	X
C-SSRS	X	X	X	X	X	X	X	X	X	X	X	X
HADS	X	X		X	X	X	X	X	X	X	X	X
Hematology/biochemistry/ urinalysis	X	X g	X	X	X	X	X	X	X	X	X	X
12-lead ECG h	X	X		X			X					X
Pregnancy testing i	X	X		X	X	X	X	X	X	X	X	X
Hepatitis B and C testing j	X											
HIV testing	X											
Chest x-ray k	X											
IGRA tuberculosis test l,m	X											X
Tuberculosis questionnaire	X	X							X			X

**Table 5–1: Schedule of assessments**

Visit a / Week  Protocol activity	Screening b	Baseline	Treatment Period (Time after the first dose)								Wk 36 EWD/ SFU c	
			Wk 2	Wk 4	Wk 8	Wk 12	Wk 16	Wk 20	Wk 24	Wk 28		
Blood sample for bimekizumab plasma concentrations n		X	X	X	X	X	X	X	X	X	X	X
Blood sample for anti-bimekizumab antibodies n		X		X	X	X	X	X	X	X	X	X
Blood sample for cytokines, complement, candidate biomarker analysis, and flow cytometry n		X			X	X	X					X
Blood sample for RNA, proteins, and metabolites biomarkers n	X	X			X	X	X				X	X
Skin biopsy o		X (2)			X (2)			X (1)			X (1)	
PASI	X	X	X	X	X	X	X	X	X	X	X	X
IGA	X	X	X	X	X	X	X	X	X	X	X	X
BSA affected by psoriasis	X	X	X	X	X	X	X	X	X	X	X	X
Concomitant medication	X	X	X	X	X	X	X	X	X	X	X	X
Adverse events	X	X	X	X	X	X	X	X	X	X	X	X
IXRS	X	X		X				X				
Subject identification card	X											
Bimekizumab or placebo administration		X		X				X				

**Table 5–1: Schedule of assessments**

Visit a / Week  Protocol activity	Screening b	Baseline	Treatment Period (Time after the first dose)							Wk 36 EWD/ SFU c
			Wk 2	Wk 4	Wk 8	Wk 12	Wk 16	Wk 20	Wk 24	

BSA=body surface area; C-SSRS= Columbia Suicide Severity Rating Scale; ECG=electrocardiogram; EWD=Early Withdrawal; FSH=follicle stimulating hormone; HADS=Hospital Anxiety and Depression Scale; HIV=human immunodeficiency virus; IGA=Investigator’s Global Assessment; IGRA=interferon-gamma release assay; IXRS=interactive voice or web response system; PASI=Psoriasis Area and Severity Index; PK=pharmacokinetics; SFU=Safety Follow-Up; TB=tuberculosis; Wk=week

a Visit windows of ±3 days from the first dose at all visits except SFU. Safety Follow-Up Visit window is -3 and +7 days.

b The Screening Period will last up to a total of 4 weeks.

c The SFU Visit will occur 20 weeks after the last dose.

d A separate Informed Consent Form is required to be completed for the extension study.

e Ensure no significant changes in medical history.

f Vital signs (blood pressures, pulse rate, and temperature) are to be measured prior to blood sampling, and prior to dosing, where applicable.

g The FSH test should only be performed on postmenopausal females who have been postmenopausal for ≥1 year and last menstrual cycle occurred <2 years ago.

h At Baseline and Weeks 4 and 16, to be performed predose.

i Pregnancy testing will be serum testing at Screening and SFU. The pregnancy test will be urine at all other visits. If the subject is entering the extension study, a urine pregnancy test will be performed at SFU.

j Subjects who have evidence of or test positive for hepatitis B by any of the following criteria: 1) positive for hepatitis B surface antigen (HBsAg+); 2) positive for anti-hepatitis B core antibody (HBcAb+) and negative for anti-hepatitis B surface antibody (HBsAb–) are excluded; a positive test for HCV is defined as: 1) positive for hepatitis C antibody (anti-HCV Ab), and 2) positive via a confirmatory test for HCV (for example, HCV polymerase chain reaction) are also excluded.

k A chest x-ray must be performed at Screening or must occur within 3 months prior to Screening and results must be available at Baseline. MMR is not acceptable.

l Includes evaluation of signs and symptoms of active TB and risk for exposure to TB.

m It is recommended that the QuantiFERON TB GOLD test be performed.

[figure not shown]
n All blood samples taken prior to dosing.

o Lesional and nonlesional biopsies to be obtained at Baseline and Week 8. Lesional biopsies to be obtained at Week 16 and Week 28.

